**Year 2: Arms 1a/1b (9-18 years of age; Pilot Phase)**

Arms 1a/1b (9-18 year olds)		Months	15.5	16				17		18		19		20		21		22		25	28
		Visits	33	34	35	36	37	38	39	40	41	42	43	44	45	46	47	48	49	50	
Procedures	Blood Volume	Study Day	434 (Rescreening)	448	451	455	462	476	490	504	518	532	546	560	574	588	602	616	700	784	
		Days post Vac	322	336/0	3	7	14	28	42	56	70	84	98	112	126	140	154	168	252	336	
		Visit Windows (days) (1)	±84	±112	±1	±2	±7	±7	±7	±7	±7	±7	±7	±7	±7	±7	±7	±7	±56	±56	
Clinical Procedures																					
Updated medical history/ physical																					
Reconsent			X																		
Pre-test/Post-test HIV counseling			X																		
Interim clinical evaluation			X	X	X	X	X	X	X	X	X	X	X	X	X	X	X	X	X	X	X
AE/SAE assessment			X	X	X	X	X	X	X	X	X	X	X	X	X	X	X	X	X	X	X
Pregnancy Prevention			X	X	X	X	X	X	X	X	X	X	X	X	X	X	X	X	X	X	X
Conmed review			X	X	X	X	X	X	X	X	X	X	X	X	X	X	X	X	X	X	X
VACCINATION			X																		
Unblinding																				X	
Feeding Evaluation (1)																					
Laboratory Procedures																					
CBC with differential	EDTA		2.0	2.0	2.0		2.0														
ALT/ Creatinine	SST		5.0	3.0	3.0		3.0														
HIV testing	SST																				
Urine/Serum pregnancy test (females only)	Urine Container or SST		X	X			X		X		X		X		X						
Malaria Blood Smear	CAP/EDTA		0.5	0.5			0.5	0.5	0.5	0.5	0.5	0.5	0.5	0.5	0.5	0.5	0.5	0.5	0.5	0.5	0.5
Malaria PCR/Genotyping/ Gametocyte	CAP/EDTA		0.5	0.5			0.5	0.5	0.5	0.5	0.5	0.5	0.5	0.5	0.5	0.5	0.5	0.5	0.5	0.5	0.5
Pfs230 ELISA	SST		5	5		5	10			5				5						5	5
SMFA (2)							X	X	X	X	X	X	X	X	X	X					
DSF (3)	X																				
Transcriptional analysis	PAXGene		1		1		1													1	
Daily blood draw volume in mL			14.0	11.0	6.0	5.0	17.0	1.0	1.0	6.0	1.0	1.0	1.0	6.0	1.0	1.0	1.0	7.0	6.0	6.0	
Cumulative blood volume in mL			186.0	197.0	203.0	208.0	225.0	226.0	227.0	233.0	234.0	235.0	236.0	242.0	243.0	244.0	245.0	252.0	258.0	264.0	
1 Visit windows are based off timing of days post the preceding vaccination; broad visit window in place for Booster dose in attempt to group VU together and provide flexibility given the ongoing COVID pandemic 2 SMFA may be completed on subjects at Study Day 448 and 504; other SMFA time points indicated above will be completed depending on associated ELISA and DSF results at that time point. 3 DSF will be completed twice monthly post Vaccination #4 from day 463 through 588 (total = 10 feeds).																					

**Year 2: Arms 3c/3d (9-18 years of age; Main Phase)**

Arms 3c/3d (9-18 year olds)		Months	13.5	14	15	16	17	18	19	20	21	22	23	24	25	26	27	28			
		Visits	24	25	26	27	28	29	30	31	32	33	34	35	36	37	38	39	40	41	
Procedures	Blood Volume	Study Day	378 (Rescreening)	392	395	399	406	420	434	448	462	476	490	504	518	532	546	560	644	728	
		Days post Vac	322	336/0	3	7	14	28	42	56	70	84	98	112	126	140	154	168	252	336	
		Visit Windows (days) (1)	±84	±112	±1	±2	±7	±7	±7	±7	±7	±7	±7	±7	±7	±7	±7	±7	±56	±56	
Clinical Procedures																					
Updated medical history/ physical																					
Reconsent			X																		
Pre-test/Post-test HIV counseling			X																		
Interim clinical evaluation			X	X	X	X	X	X	X	X	X	X	X	X	X	X	X	X	X	X	X
AE/SAE assessment			X	X	X	X	X	X	X	X	X	X	X	X	X	X	X	X	X	X	X
Pregnancy Prevention			X	X	X	X	X	X	X	X	X	X	X	X	X	X	X	X	X	X	X
Conmed review			X	X	X	X	X	X	X	X	X	X	X	X	X	X	X	X	X	X	X
VACCINATION			X																		
Unblinding																					X
Feeding Evaluation (1)																					X
Laboratory Procedures																					
CBC with differential	EDTA		2.0	2.0	2.0		2.0														
ALT/ Creatinine	SST		5.0	3.0	3.0		3.0														
HIV testing	SST																				
Urine/Serum pregnancy test (females only)	Urine Container or SST		X	X			X		X		X		X		X						
Malaria Blood Smear	CAP/EDTA		0.5	0.5			0.5	0.5	0.5	0.5	0.5	0.5	0.5	0.5	0.5	0.5	0.5	0.5	0.5	0.5	0.5
Malaria PCR/Genotyping/ Gametocyte	CAP/EDTA		0.5	0.5			0.5	0.5	0.5	0.5	0.5	0.5	0.5	0.5	0.5	0.5	0.5	0.5	0.5	0.5	0.5
Pfs230 ELISA	SST		5	5		5	10			5				5						5	5
SMFA (2)							X	X	X	X	X	X	X	X	X	X					
DSF (3)	X						X	X	X	X	X	X	X	X	X	X					
Transcriptional analysis	PAXGene		1		1		1														1
Daily blood draw volume in mL			14.0	11.0	6.0	5.0	17.0	1.0	1.0	6.0	1.0	1.0	1.0	6.0	1.0	1.0	1.0	7.0	6.0	6.0	6.0
Cumulative blood volume in mL			174.5	185.5	191.5	196.5	213.5	214.5	215.5	221.5	222.5	223.5	224.5	230.5	231.5	232.5	233.5	240.5	246.5	252.5	252.5
1 Visit windows are based off timing of days post the preceding vaccination; broad visit window in place for Booster dose in attempt to group VU together and provide flexibility given the ongoing COVID pandemic 2 SMFA may be completed on subjects at Study Day 336 and 448; other SMFA time points indicated above will be completed depending on associated ELISA and DSF results at that time point. 3 DSF will be completed twice monthly post Vaccination #4 from day 406 through 532 (total = 10 feeds).																					

Year 2: Arms 3e/3f (≥19 years of age)

Arms 3e/3f (Adults 19 years of age and older)		Months	13.5	14				15	16	18	20	23	26
		Visits	24	25	26	27	28	29	30	31	32	33	34
Procedures	Blood Volume	Study Day	378 (Rescreening)	392	395	399	406	420	448	504	560	644	728
		Days post Vac	322	336/0	3	7	14	28	56	112	168	252	336
		Visit Windows (days) (1)	±84	±112	±1	±2	±7	±7	±7	±7	±28	±56	±56
Clinical Procedures													
Updated medical history/ physical													
Reconsent			X										
Pre-test/Post-test HIV counseling			X										
Interim clinical evaluation			X	X	X	X	X	X	X	X	X	X	X
AE/SAE assessment			X	X	X	X	X	X	X	X	X	X	X
Pregnancy Prevention			X	X	X	X	X	X	X	X	X	X	X
Conmed review			X	X	X	X	X	X	X	X	X	X	X
VACCINATION			X										
Unblinding											X		
Laboratory Procedures													
CBC with differential	EDTA		2	2	2		2						
ALT/ Creatinine	SST			3	3		3						
HIV testing	SST		5										
Urine/Serum pregnancy test (females only)	Urine Container or SST		0.5	X									
Malaria Blood Smear	CAP/EDTA		0.5	0.5			0.5		0.5	0.5	0.5	0.5	0.5
Malaria PCR/Genotyping/ Gametocyte	CAP/EDTA		0.5	0.5			0.5		0.5	0.5	0.5	0.5	0.5
Pfs230 ELISA	SST		5	5		5	10		5	5	5	5	5
SMFA (2)													
Transcriptional analysis	PAXGene		1		1		1				1		
Daily blood draw volume in mL			12.5	11.0	6.0	5.0	17.0	0.0	6.0	6.0	7.0	6.0	6.0
Cumulative blood volume in mL			161.0	172.0	178.0	183.0	200.0	200.0	206.0	212.0	219.0	225.0	231.0
1 Visit windows are based off timing of days post the preceding vaccination; broad visit window in place for Booster dose in attempt to group VU together and provide flexibility given the ongoing COVID pandemic													
2 SMFA may be completed on subjects at Study Day 392 and 448; other SMFA time points indicated above will be completed depending on associated ELISA results at that time point.													

## **Appendix B: Day to Day Schedule by Arms**

### **Arms 4a/4b (1-4 year olds): No Vaccination**

#### **Study Day -14 ( $\pm 0$ days; Drug Treatment Visit; should align with Vaccine Unit visit prior to Vaccination #3)**

The following evaluations/procedures will be completed before vaccination:

1. Perform basic history and focused physical examination, emphasizing examination of any acute complaints.
2. Record vital signs (blood pressure, temperature, and heart rate).
3. Record AEs and concomitant medications, if applicable.
4. Obtain approximately 1.5 mL of blood for malaria blood smear and malaria PCR.
5. Administer first dose of artemether/lumefantrine (AL).
  - a. Additional doses of AL will occur on study days -13, -12

#### **Study Day 0 ( $\pm 7$ day)**

1. Perform basic history and focused physical examination, emphasizing examination of any acute complaints.
2. Record vital signs (blood pressure, temperature, and heart rate).
3. Record AEs and concomitant medications, if applicable.
4. Obtain approximately 1.5 mL of blood for malaria blood smear and malaria PCR.

#### **Study Day 1 ( $\pm 0$ day)**

1. Perform basic history and focused physical examination, emphasizing examination of any acute complaints.
2. Record vital signs (blood pressure, temperature, and heart rate).
3. Record AEs and concomitant medications, if applicable.
4. Obtain approximately 1.5 mL of blood for malaria blood smear and malaria PCR.

#### **Study Day 3 ( $\pm 1$ day)**

1. Perform basic history and focused physical examination, emphasizing examination of any acute complaints.
2. Record vital signs (blood pressure, temperature, and heart rate).
3. Record AEs and concomitant medications, if applicable.
4. Obtain approximately 1.5 mL of blood for malaria blood smear and malaria PCR.

#### **Study Day 7 ( $\pm 2$ day)**

1. Perform basic history and focused physical examination, emphasizing examination of any acute complaints.
2. Record vital signs (blood pressure, temperature, and heart rate).
3. Record AEs and concomitant medications, if applicable.
4. Obtain approximately 1.5 mL of blood for malaria blood smear and malaria PCR.

#### **Study Day 14 ( $\pm 7$ day)**

1. Perform basic history and focused physical examination, emphasizing examination of any acute complaints.
2. Record vital signs (blood pressure, temperature, and heart rate).
3. Record AEs and concomitant medications, if applicable.
4. Obtain approximately 1.5 mL of blood for malaria blood smear and malaria PCR.

**Study Day 28 (±7 day)**

1. Perform basic history and focused physical examination, emphasizing examination of any acute complaints.
2. Record vital signs (blood pressure, temperature, and heart rate).
3. Record AEs and concomitant medications, if applicable.
4. Obtain approximately 1.5 mL of blood for malaria blood smear and malaria PCR.

**Study Day 42 (±7 day)**

1. Perform basic history and focused physical examination, emphasizing examination of any acute complaints.
2. Record vital signs (blood pressure, temperature, and heart rate).
3. Record AEs and concomitant medications, if applicable.
4. Obtain approximately 1.5 mL of blood for malaria blood smear and malaria PCR.

**Study Day 56 (±7 day)**

1. Perform basic history and focused physical examination, emphasizing examination of any acute complaints.
2. Record vital signs (blood pressure, temperature, and heart rate).
3. Record AEs and concomitant medications, if applicable.
4. Obtain approximately 1.5 mL of blood for malaria blood smear and malaria PCR.

**Study Day 70 (±7 day)**

1. Perform basic history and focused physical examination, emphasizing examination of any acute complaints.
2. Record vital signs (blood pressure, temperature, and heart rate).
3. Record AEs and concomitant medications, if applicable.
4. Obtain approximately 1.5 mL of blood for malaria blood smear and malaria PCR.

**Study Day 84 (±7 day)**

1. Perform basic history and focused physical examination, emphasizing examination of any acute complaints.
2. Record vital signs (blood pressure, temperature, and heart rate).
3. Record AEs and concomitant medications, if applicable.
4. Obtain approximately 1.5 mL of blood for malaria blood smear and malaria PCR.

**Study Day 98 (±7 day)**

1. Perform basic history and focused physical examination, emphasizing examination of any acute complaints.
2. Record vital signs (blood pressure, temperature, and heart rate).
3. Record AEs and concomitant medications, if applicable.
4. Obtain approximately 1.5 mL of blood for malaria blood smear and malaria PCR.

**Study Day 112 (±7 day)**

1. Perform basic history and focused physical examination, emphasizing examination of any acute complaints.
2. Record vital signs (blood pressure, temperature, and heart rate).
3. Record AEs and concomitant medications, if applicable.
4. Obtain approximately 1.5 mL of blood for malaria blood smear and malaria PCR.

**Study Day 126 (±7 day)**

1. Perform basic history and focused physical examination, emphasizing examination of any acute complaints.
2. Record vital signs (blood pressure, temperature, and heart rate).
3. Record AEs and concomitant medications, if applicable.
4. Obtain approximately 1.5 mL of blood for malaria blood smear and malaria PCR.

**Study Day 140 (±7 day)**

1. Perform basic history and focused physical examination, emphasizing examination of any acute complaints.
2. Record vital signs (blood pressure, temperature, and heart rate).
3. Record AEs and concomitant medications, if applicable.
4. Obtain approximately 1.5 mL of blood for malaria blood smear and malaria PCR.

**Study Day 154 (±7 day)**

1. Perform basic history and focused physical examination, emphasizing examination of any acute complaints.
2. Record vital signs (blood pressure, temperature, and heart rate).
3. Record AEs and concomitant medications, if applicable.
4. Obtain approximately 1.5 mL of blood for malaria blood smear and malaria PCR.

**Study Day 168 (±28 day)**

1. Perform basic history and focused physical examination, emphasizing examination of any acute complaints.
2. Record vital signs (blood pressure, temperature, and heart rate).
3. Record AEs and concomitant medications, if applicable.
4. Obtain approximately 1.5 mL of blood for malaria blood smear and malaria PCR.

**Study Day 252 (±56 day)**

1. Perform basic history and focused physical examination, emphasizing examination of any acute complaints.
2. Record vital signs (blood pressure, temperature, and heart rate).
3. Record AEs and concomitant medications, if applicable.
4. Obtain approximately 1.5 mL of blood for malaria blood smear and malaria PCR.

**Study Day 378 (±84 day)**

1. Reconsent for continuation on study.
2. Perform updated medical history and physical examination, emphasizing examination of any acute complaints.
3. Record vital signs (weight, length, blood pressure, temperature, and heart rate).
4. Record AEs and concomitant medications, if applicable.
5. Obtain approximately 1 mL of blood for malaria blood smear and malaria PCR.
6. Administer first dose of artemether/lumefantrine (AL).
  - a. Additional doses of AL will occur on study days -13, -12.

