If there are no safety concerns, in a staggered manner, the main phase will begin enrollment of approximately 137 compounds/vaccine units (~1500 vaccinees + ~400 under 5 years of age for parasite surveillance). Children enrolled during the pilot safety phase will join their main phase compounds/family for vaccination #3. Prior to receipt of first vaccination, all subjects will receive a full treatment course of AL. All vaccinated subjects will be monitored for safety and tolerability. Immunogenicity outcomes will be antibody responses as measured by enzyme-linked immunosorbent assay (ELISA) against recombinant Pfs230D1M. Functional activity of the induced antibodies will be assessed by standard membrane feeding assays in select samples. Vaccine activity will be measured in children 9-18 years of age who will undergo direct skin feeds (DSF) starting 2 weeks post vaccination #3 for a total of 8 DSFs.

Prior to scheduled last vaccination in members of the compound/family, children 1-4 years of age and vaccinated children 5-8 years of age will receive a full treatment course of AL prior to the expected start of the transmission season and will then be followed every 2 weeks by blood smear (BS) along with all vaccinated children. Children 9-18 years of age will also be assessed for vaccine efficacy, but as a separate analysis from those 1-8 years of age.

In Year 2, those who received vaccination during Year 1 (5 years of age and older at enrollment), if eligible and still on study, will receive a single fourth vaccination per their vaccine unit (VU) blinded arm assignment. No new individuals will be enrolled. Again, children 1-4 years of age and vaccinated children 5-8 years of age will receive a full treatment course of AL prior to the expected start of the transmission season and will then be followed every 2 weeks by BS along with all vaccinated children. Children 9-18 years of age will also be assessed for vaccine efficacy against parasitemia, but as a separate analysis from those 1-8 years of age. Immunogenicity outcomes will be antibody responses as measured by ELISA against recombinant Pfs230D1M. Functional activity of the induced antibodies will be assessed by standard membrane feeding assays in select samples. Vaccine activity will be measured in children 9-18 years of age who will undergo DSF starting 2 weeks post vaccination #4 for a total of 10 DSFs.

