administered prior, subject to clinician's discretion. Children 1-4 years of age will be enrolled just before the malaria transmission season and will receive AL concomitantly with children 5-8 years of age who will be treated ~14 days before the 3rd vaccine dose and ~7 days prior to vaccination #4. All enrolled subjects (except adults,  $\geq 19$  years old) will be monitored for patent parasitemia every 2 weeks, and all enrolled subjects during unscheduled visits if clinically indicated, for at least 6 months up to 12 months post vaccination, with time to patent parasitemia being evaluated as a vaccine efficacy timepoint in children 1-8 years of age as well as 9-18 years of age within the compounds (separate secondary evaluation given expected nighttime mobility and no pre-transmission season AL treatment). Preteen and adolescent subjects will also be assessed by DSF for vaccine activity starting 2 weeks post receipt of vaccination #3 and post receipt of vaccination #4; DSFs will be completed every 2 weeks for a total of 8 DSF (post vaccination #3) and for a total of 10 DSF (post vaccination #4).

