**Table 12. Approximate Census Counts in Doneguebougou in June 2018.**

Age (years)	<1	1-4	5-8	9-18	19+
Population	29	295	229	584	867
Actual Enrollment	0	192	215	399	495

**Group 3** (n~1500): Pfs230D1M-EPA/AS01 or comparator vaccine

- **Arm 3a:** 5-8 years of age to receive 40 µg of Pfs230D1M-EPA/AS01 on days 0, 28, 56, 392; receipt of AL on day -7, 42, and 385
- **Arm 3b:** 5-8 years of age to receive HAVRIX (day 0, 392), TYPHIM Vi (day 28), Menactra (day 56); receipt of AL on day -7, 42, and 385
- **Arm 3c:** 9-18 years of age to receive 40 µg of Pfs230D1M-EPA/AS01 on days 0, 28, 56, 392; receipt of AL on day -7
- **Arm 3d:** 9-18 years of age to receive HAVRIX (day 0, 392), TYPHIM Vi (day 28), Menactra (day 56); receipt of AL on day -7
- **Arm 3e:** 19 years of age or older to receive 40 µg of Pfs230D1M-EPA/AS01 on days 0, 28, 56, 392; receipt of AL on day -7
- **Arm 3f:** 19 years of age or older to receive HAVRIX (day 0, 392), TYPHIM Vi (day 28), Menactra (day 56); receipt of AL on day -7

**Group 4** (n=400): blood smear + AL treatment (parasitemia)

- **Arm 4a:** 1-4 years of age residing with/in same families/compounds as Arms 1a, 2a, 3a, 3c, 3e (Pfs230D1M-EPA/AS01 compounds) receipt of AL on day -14, 385
- **Arm 4b:** 1-4 years of age residing with/in same families/compounds as Arms 1b, 2b, 3b, 3d, 3f (comparator compounds) receipt of AL on day -14, 385

To ensure further safety, family compounds will be enrolled in a staggered manner with acceleration over time, with a planned DSMB review after approximately 1/3 enrollment (~30 family compounds/vaccine units). Five compounds will be enrolled within the first 1-2 days of the main phase enrollment, then will await 2 days from first vaccination in that wave of enrollment until enrolling an additional 10 compounds over 1-2 days. Following waiting at least 2 days from the first vaccination during that second wave of enrollment, a final additional 15 compounds will be enrolled. Given our current estimates of family compound make up, this initial study enrollment (Pilot Phase) will result in an additional vaccination of a smaller subset of 5-8 years of age and 9-18 years of age for extra safety data prior to accelerated enrollment of the remaining family compounds ~1 week later.

Children in Arms 2a/2b, 3a/3b, and 4a/4b (1-8 years of age) will also receive a treatment course of AL ~14 days prior to the time of vaccination #3 in the relevant Arms (AL dosing prior to

[figure not shown]

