#### **11.1.2 Screening for Arm 4**

The following screening evaluations must be completed for all subjects within the 56 days prior to enrollment (Arm 4):

- Explain the study and informed consent documents to parent/guardian. (Year 1 + 2)
- Ensure that the parent/guardian has acknowledged consent by signing or fingerprinting the consent document and that the parent/guardian acknowledges permission for the subject to participate by signing or fingerprinting the informed consent form. Ensure that the parent/guardian receives a signed copy of the informed consent. (Year 1 + 2)
- Ensure the subject's parent/guardian has correctly answered  $\geq 80\%$  of the questions on the Malaria Comprehension Exam. (Year 1 only)
- Elicit a complete medical history and medication use. (Year 1 + 2)
- Administer a complete physical examination, including vital signs (blood pressure, temperature, and heart rate), height/length, and weight. (Year 1 + 2)
- Obtain a 12-lead electrocardiogram (EKG). (Year 1 only)

If initial screening is completed  $>56$  days prior to Study Day 0, the following screening procedures will need to be repeated before enrollment: repeat a new Malaria Comprehension Exam, updated medical history, repeat physical exam, and repeat EKG. Subjects will then be reassessed for eligibility based on the re-screening information.

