**Year 2: Arms 4a/4b (1-4 years of age)**

Arms 2a/2b (5-8 year olds)		Months	13.5		14		15		16		17		18		19		20	23	26
		Visits	29	30	31	32	33	34	35	36	37	38	39	40	41	42	43	44	45
Procedures	Blood Volume	Study Day	378 (Rescreening)	385	392	406	420	434	448	462	476	490	504	518	532	546	560	644	728
		Days Post Vac	322	329	336/0	14	28	42	56	70	84	98	112	126	140	154	168	252	336
		Visit Windows (days) (1)	±84	±14	±112	±14	±14	±14	±14	±14	±14	±14	±14	±14	±14	±14	±14	±14	±56
Clinical Procedures																			
Updated medical history/ physical			X																
Reconsent			X																
Interim clinical evaluation				X	X	X	X	X	X	X	X	X	X	X	X	X	X	X	X
AE/SAE assessment			X	X	X	X	X	X	X	X	X	X	X	X	X	X	X	X	X
Conmed review			X	X	X	X	X	X	X	X	X	X	X	X	X	X	X	X	X
Artemether/Lumefantrine				X															
Unblinding (VU)																	X		
Laboratory Procedures																			
Malaria Blood Smear	CAP/EDTA		0.5	0.5	0.5	0.5	0.5	0.5	0.5	0.5	0.5	0.5	0.5	0.5	0.5	0.5	0.5	0.5	0.5
Malaria PCR/Genotyping/ Gametocyte	CAP/EDTA		0.5	0.5	0.5	0.5	0.5	0.5	0.5	0.5	0.5	0.5	0.5	0.5	0.5	0.5	0.5	0.5	0.5
Daily blood draw volume in mL			1	1	1	1	1	1	1	1	1	1	1	1	1	1	1	1	1
Cumulative blood volume in mL			150.5	151.5	152.5	153.5	154.5	155.5	156.5	157.5	158.5	159.5	160.5	161.5	162.5	163.5	164.5	165.5	166.5
1 Visit windows are based off timing of days post the preceding vaccination; broad visit window in place for Booster dose in attempt to group VU together and provide flexibility given the ongoing COVID pandemic; increased visit windows for visits to align with parental visits																			

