**Study Day 385 (±14 day)**

1. Perform basic history and focused physical examination, emphasizing examination of any acute complaints.
2. Record vital signs (blood pressure, temperature, and heart rate).

3. Record AEs and concomitant medications, if applicable.
4. Obtain approximately 1 mL of blood for malaria blood smear and malaria PCR.
5. Administer first dose of artemether/lumefantrine (AL).
6. Additional doses of AL will occur on study days 386, 387.

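### Appendix B starts artemether/lumefantrine twice in Year 2 for the unvaccinated children aged 1-4 (Day 378 and Day 385), while the design gives them one course, at Day 385

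*Combined protocol and SAP*

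**What the plan says.** Appendix B, Arms 4a/4b, contains two Year 2 visits that each start AL.

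- **Study Day 378 (±84 days), reconsent and rescreening.** Step 6 reads "Administer first dose of artemether/lumefantrine (AL"), and step 6a adds "Additional doses of AL will occur on study days -13, -12".
- **Study Day 385 (±14 days).** Step 5 starts AL again, and step 6 reads "Additional doses of AL will occur on study days 386, 387".

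The rest of the protocol describes one Year 2 course for these children.

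- The Protocol Summary and Section 7.2.2 list, for both arms, "receipt of AL on day -14, 385".
- Section 7.1 ties their AL to that of the children aged 5-8, "who will be treated ~14 days before the 3rd vaccine dose and ~7 days prior to vaccination #4".
- The Précis, on Year 2, says "Again, children 1-4 years of age and vaccinated children 5-8 years of age will receive a full treatment course of AL", in the singular.
- The Appendix A grid headed "Year 2: Arms 4a/4b (1-4 years of age)" has one mark in the AL row, one column to the right of rescreening.
- Section 11.1.2, the screening list for Arm 4, marks which items apply in Year 2 (for example "Elicit a complete medical history and medication use. (Year 1 + 2)") and does not include AL.

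**The concern.** Section 11 describes Appendix A as the summary of the schedule and Appendix B as the detail. Appendix B is therefore the text a clinic would work from visit by visit, and an error there is an operative dosing instruction. Staff following it would start AL at rescreening and again at the next visit, in children aged 1-4 who are treated whether or not they have malaria.

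Sections 18.4.2 and 12.4 treat a prolonged QTc as a reason to exclude, yet the screening EKG is a Year 1 procedure, repeated in Year 2 only if health or medication has changed. An unplanned exposure would not normally be preceded by a new EKG.

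AL also sets the cleared starting point for Year 2 parasitemia follow-up in ages 1-8. Extra or mistimed doses would blur that starting point equally in both arms.

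**Working it through.** There is no statistical figure in the plan to reproduce. The check compares the schedules and counts days.

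**Inputs**

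- AL starts at Day 378 and Day 385, with windows of ±84 and ±14 days (Appendix B, Arms 4a/4b).
- Fourth vaccination of the main-phase units at Day 392 (Protocol Summary, Section 7.2.2).
- One AL course is one dosing day on each of 3 consecutive days (Section 18.4.2).
- Children enrolled in Arms 4a/4b: 192 (Table 7, Table 12). The number continuing into Year 2 is not given.

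**Which day the design intends.** Section 7.1 puts the Year 2 course about 7 days before vaccination #4: 392 − 7 = 385. This agrees with the Protocol Summary and Section 7.2.2. For ages 5-8, the Appendix B rescreening visit (Day 434 pilot, Day 378 main) has no AL step, and AL comes only at Day 441/385. The Day 378 step in Arms 4a/4b therefore stands alone.

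**Where the Day 378 follow-on days come from.** The Year 1 AL visit for these arms is Day -14, with follow-on doses on Days -13 and -12. Step 6a at Day 378 repeats those numbers, which suggests that the Year 1 text was carried over; that origin is an inference. As study days they lie more than a year before the visit. Counted back from Day 392 they would be 392 − 13 = 379 and 392 − 12 = 380.

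**Year 2 dosing days per child, with the two visits on different days**

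| Reading | Dosing days | Total | Unplanned |
|---|---|---|---|
| Design | 385, 386, 387 | 3 | 0 |
| Appendix B, follow-on days at 378 unusable | 378; 385, 386, 387 | 4 | 1 |
| Appendix B, follow-on days taken as 379 and 380 | 378, 379, 380; 385, 386, 387 | 6 | 3 |

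On the second row the child gets a single dose at Day 378, which is not a complete course. On the third, a complete course ends on Day 380 and another begins 385 − 380 = 5 days later.

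**Ceiling across the cohort.** 192 × 1 = 192 unplanned dosing days, or 192 × 3 = 576.

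**Spacing of the two starts.** Nominally 385 − 378 = 7 days. The windows are 378 ± 84 = 294 to 462 and 385 ± 14 = 371 to 399. With rescreening first, the gap can run from 0 to 399 − 294 = 105 days.

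**Effect of the correction.** Removing the AL step at Day 378 leaves Days 385-387 in Year 2 and two courses over the study (Day -14 and Day 385), as the Protocol Summary states.

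**The case against.** The best case on the other side is that this is a clerical slip. The design is stated consistently elsewhere, no design decision is in doubt, and two consecutive visits that each call for a first dose, one with negative follow-on days, would probably prompt a query. AL is licensed with an acceptable safety profile, and children with a QTc above 450 ms were excluded at Year 1 screening. It is fair to call the error a drafting contradiction. That a site would query it is a hope, and the protocol should not depend on it.

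The size is also uncertain. If rescreening and the AL visit fall on the same day, which the windows allow, the two lines collapse into one start and nothing extra is given. The choice between 192 and 576 depends on how staff resolve an unclear line, and 192 is Year 1 enrollment. These points stand: the figures are ceilings, and the 105-day gap is an extreme of the windows.

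Some of the corroboration is weak. The Year 2 grid carries a header for Arms 2a/2b under its Arms 4a/4b title, and its cumulative blood volumes do not follow from the Year 1 table for these children. The screening list for Arms 1-3 omits AL as well, so its absence from the Arm 4 list shows little. The contradiction does not need either source, because the Protocol Summary, the Précis and Sections 7.1 and 7.2.2 are enough.

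Finally, Section 18.4.2 already requires AL dosing and its timing to be documented, so part of the remedy is in place.

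**Conclusion.** The concern holds. Appendix B instructs staff to start AL at Day 378 and at Day 385 in Arms 4a/4b, the design calls for Day 385 only, and no text makes the first conditional on anything or a substitute for the second.

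When the two visits fall on different days, following the text gives each continuing child one unplanned dosing day, or three on the fuller reading. The cohort ceilings of 192 and 576 assume that all 192 enrolled children continue and that none has the two visits on the same day. The documents do not show whether any child was in fact dosed twice.

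The comparison of 4a with 4b is not biased by the text, because the instruction is the same in both arms, and no sample-size or power figure is affected. The correction is necessary because a dosing instruction for young children contradicts the design.

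**What to change.** In Appendix B, Arms 4a/4b, Study Day 378, delete steps 6 and 6a. Leave the Day 385 visit as the only Year 2 AL start, with follow-on doses on Days 386 and 387. Send the site a memo stating this. From the dosing records already required, list the Year 2 AL dates each child actually received, so that any extra exposure is known to the safety reviewers and to the parasitemia analysis.

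In the same edit, the heading of the Day 441/385 AL visit for ages 5-8, which labels it as the day of the fourth vaccination, can be corrected; that changes no treatment.

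The cost is two deleted lines, one site memo and a listing from existing records. No visit, sample size or analysis changes.
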